### Exclusion criteria:

4.1 Patients with previous history of hypersensitivity to ribavirin or its components

4.2 Women who are pregnant or plan a pregnancy within 8 weeks after completion of treatment (only for patients who are going to be randomised to either therapeutic arms).

4.3 Patients with evidence of RSV LRI as documented by a positive rapid RSV antigen testing and/or culture on nasal washes **AND** new or progressive infiltrates on chest radiographic studies suggestive of viral etiology and/or pulse oxygen less than 90 mm of Hg on room air.

4.4 Patients with positive RSV by rapid antigen testing and/or culture in bronchoalveolar lavage regardless of the chest radiographic findings at study entry.

4.5 Patients who are considered to be moderately or severely anemic as per the NCI classification will not be included in the study, i.e patients with hemoglobin level less than 8 g/dl.

4.6 Patients with Total Bilirubin, Aspartate Aminotransferase (AST) and/or Alanine Aminotransferase (ALT) three times the upper limit of normal.

4.7 Male partners of women who are pregnant (only for patients who are going to be randomised to either therapeutic arms).

4.8 Patients with known history of autoimmune hepatitis, Hepatitis C or those with hemoglobinopathies (eg, thalassemia major, sickle cell anemia).

4.9 Patients with creatinine clearance less than or equal to 50 ml/min.

5.0 Patients taking didanosine, azthioprine, or nucleoside reverse transcriptase inhibitors.

Patients who will be enrolled on the observational arm have to meet inclusion criteria #4.2, 4.3, and 4.4 and exclusion criteria #4.3 and 4.4 only as these patients will not receive therapy for RSV.

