### **3.0 Background Drug Information and Dosage**

Ribavirin in its oral or aerosolized form is commercially available. Drug information is provided in the attached package insert (Appendix D).

Oral ribavirin has been used at varying doses for treatment of RSV based on bioavailability and a large volume of distribution. A loading dose of 10 mg/kg orally has been used as bioavailability can range from 30-74% due to first pass metabolism (*Khanna N, et al. Clin Infect Dis. 2008;46(3):402-412*). Due to the short duration of therapy, 5 to 10 days, this will help to increase ribavirin concentration more quickly. After the loading dose, a total daily dose of 20 mg/kg/day divided into three doses given with food (max dose of 1800 mg per day). This dosing strategy falls within a previous efficacy and toxicity trial where doses between 15-45 mg/kg/day were employed (*Chakrabarti S, et al. Bone Marrow Transplant. 2001;28(8):759-763*). Efficacy and decreased toxicity were found in the lower dose cohorts 15-30 mg/kg/day.

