## 4.0 Patient Eligibility

### Inclusion criteria:

4.1 HSCT patients with either moderate risk or high risk immunodeficiency based on immunodeficiency scoring system would be eligible for entry on study if a nasopharyngeal wash or throat swab specimen is positive by rapid RSV antigen testing and/or on culture within 72 hours (therapeutic arms). (Please see Appendix E for definitions and Immunodeficiency Scoring)

4.2 HSCT patients with low risk immunodeficiency based on immunodeficiency scoring system would be eligible for entry on study if a nasopharyngeal wash or throat swab specimen is positive by rapid RSV antigen testing and/or on culture within 72 hours but will not be randomized to therapeutic arms and will be followed as per standard of care (observational arm).

4.3 Patients must be at least 18 years of age and able to swallow pills.

4.4 Patients with RSV infection limited to the URT as documented by negative Chest radiographic findings within the last 48 hours of enrollment and pulse oxygenation of more than 90 mm of Hg on room air.

4.5 Women of child bearing potential with a negative urine or blood pregnancy test within a month of enrollment (only for patients who are going to be randomised to either therapeutic arms).

4.6 Patients with Hemoglobin levels more than or equal to 8 g/dl would be eligible for the study even if they are currently receiving blood products.

4.7 Patients may receive up to 2 doses of aerosolized ribavirin on the modified regimen before enrollment into the study.

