## **6.0 Pretreatment evaluation**

6.1 Patients will be identified based on eligibility criteria. After a patient is identified and expresses interest, the study will be explained by the study team and the informed consent form will be given to the patient to be signed.

6.2 All patients should have an initial nasopharyngeal wash positive for RSV by rapid testing and/or culture at onset of therapy unless a positive result was obtained from a specimen during the preceding 72 hours.

6.3 Routine blood tests will be obtained as per the standard of care within 48 hours of study entry as follows:

A. Hemoglobin, Hematocrit, WBC with differential if available, platelets count, pregnancy test from urine or blood for women of child-bearing potential.

B. Chemistry profile – BUN, Creatinine, Total bilirubin, Aspartate Aminotransferase (AST) and/or Alanine Aminotransferase (ALT), and alkaline phosphatase.

C. Nasal washes and blood at the time of enrollment will be taken and saved for testing for RSV viral loads and titers and neutralizing antibodies in serum at a later date (see section 7.1).

6.4 An initial history and physical examination.

6.5 A chest radiographic study (i.e. chest radiographs and/or CT scan of chest) will be obtained if not done within preceding 48 hours as per standard of care.

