## **7.0 Evaluation During Study**

7.1 Nasal washes for the therapeutic arm will be repeated on day 3  $\pm$  1 day, day 7 ( $\pm$  1 days), day 14 ( $\pm$  1 days), and by day 14  $\pm$  1 days after end of therapy; and will be stored at 6-8 degrees Celsius until it can be taken to [name] laboratory for analysis. Blood specimens for the therapeutic arm will be drawn at enrollment and 14  $\pm$  1 days after end of therapy. These specimens will be shipped for batch analysis to [name] laboratory at Baylor College of Medicine ([name]) for viral loads, titers and for neutralizing antibodies testing (Please see references 7-9 for methods). For patients on the observational arm, nasal washes for RSV viral loads will be done once a week for 4 weeks and blood specimens will be taken at enrollment and the 4th week on study for neutralizing antibodies testing and for RSV viral load. Leftover of blood and nasal washes will be saved at [name] laboratory for future testing.

7.2 Routine blood tests as in 6.3 will be repeated at least once weekly until study is completed as part of the standard of care for patients who are on the therapeutic arms. Patients on observational arm will have routine blood tests done at enrollment and the 4th week on study.

7.3 Patients will be monitored for signs and symptoms of URI and LRI (Please see Appendix G and H for Clinical Assessment Tool). Patients who are hospitalized will be seen 2 times a week from the time of enrollment until discontinuation of ribavirin therapy. Patients who are not hospitalized will be monitored twice a week until the discontinuation of therapy or once a week for 4 weeks for patients on the observational arm. Any possible evidence of pulmonary infection should be confirmed by a repeat chest radiographic study and/or oxygen saturation level. All patients on the therapeutic arms will have a final visit 14 days  $\pm$  1 days after end of therapy.

7.4 Follow-up after end of therapy or discontinuation of therapy: Patients will be seen 14 days  $\pm$  1 days after discontinuation of therapy for the final determination of response, unless there is progression to pneumonia. In the latter scenario or if study drug is discontinued for Serious Adverse Events (SAEs), patients will be followed for up to 14 days from the time of occurrence of the event or until resolution of the SAE whichever occurs last or up to 30 days from the last dose of the study drug.

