7.5 Physical Exams for the therapeutic arm will be done at day 3  $\pm$  1 day, day 7 ( $\pm$  1 days), day 14 ( $\pm$  1 days), and then 14 days ( $\pm$  1 days) after end of therapy. Concomitant medications that are used to treat LRI will be recorded day (3  $\pm$  1 day), day 7 ( $\pm$  1 days), and then at 14 days ( $\pm$  1 days) after end of therapy. Physical exams for observational arm will be done once a week for 4 weeks.

7.6 As standard of care, patients will have pulmonary function tests scheduled between 6-10 weeks after completing therapy for RSV.

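### Exclusion 4.7 bars randomised men only for an existing partner pregnancy, so a man planning to conceive during or soon after ribavirin is eligible under section 4.0 as written

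*Combined protocol and SAP*

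**What the plan says.** Section 4.0 of the combined protocol and SAP has two reproductive exclusions, both limited to patients who will be randomised. Inclusion and exclusion criteria share the same numbers; those meant here are exclusions 4.2 and 4.7.

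- Exclusion 4.2, for women: "Women who are pregnant or plan a pregnancy within 8 weeks after completion of treatment".
- Exclusion 4.7, for men: "Male partners of women who are pregnant (only for patients who are going to be randomised to either therapeutic arms".

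The closing line of section 4.0 frees observational patients from both. Of the exclusions, they need to satisfy "exclusion criteria #4.3 and 4.4 only as these patients will not receive therapy for RSV".

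The other reproductive provisions are pregnancy tests. Inclusion 4.5 admits "Women of child bearing potential with a negative urine or blood pregnancy test within a month of enrollment", and section 6.3A lists a "pregnancy test from urine or blood for women of child-bearing potential". Section 3.0 refers to the product information: "Drug information is provided in the attached package insert (Appendix D".

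**The concern.** The two exclusions do not cover the same ground. Rule 4.2 looks at the present and at the 8 weeks after treatment. Rule 4.7 looks only at the present. Yet the protocol treats a man's ribavirin treatment as relevant to a partner's pregnancy (4.7), and conception in the weeks after treatment as a reason not to randomise (4.2). Where the two meet, in a treated man who intends to conceive soon afterwards, neither rule applies.

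What is at stake is a patient-safety rule at screening. Section 6.1 says patients are identified from the eligibility criteria, so staff who follow section 4.0 to the letter have no reason to ask a man about his plans. The trial's statistical conclusions are not at stake.

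**Working it through.** No formula applies, because the point depends on no error rate, margin, event rate or sample size. The check is a comparison of the two rules, followed by a search of the remaining sections for anything that closes the gap.

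**Step 1. The two exclusions side by side.**

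| Feature | Women (exclusion 4.2) | Men (exclusion 4.7) |
|---|---|---|
| Pregnancy existing at entry | excluded | excluded, if the partner's |
| Pregnancy planned after treatment | excluded | not mentioned |
| Period after treatment | 8 weeks | none given |
| Who is covered | randomised patients only | randomised patients only |

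**Step 2. What both rules are tied to.** Both are limited to the randomised arms. The closing line of section 4.0 explains the shorter list of criteria for observational patients by the fact that they get no RSV therapy. So the protocol itself links both rules to ribavirin treatment. No outside drug information is needed to see that the male rule stops short of the female one.

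**Step 3. Other sections that might close the gap.**

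- Inclusion 4.5 and section 6.3A: pregnancy tests, for women only.
- Section 5.0: dosing, bronchodilators and management of progression; no conception rule.
- Section 7.0: samples, visits and examinations; no mention of conception or contraception for either sex.
- Section 9.0: removal for pulmonary infection, adverse events or anaemia; no pregnancy-related rule.

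**Step 4. The rules applied to two cases.** Take a woman of child-bearing potential with a negative test who plans a pregnancy 6 weeks after treatment: 4.2 excludes her. Take a man whose partner is not pregnant and who plans to conceive 6 weeks after treatment: 4.7 does not exclude him, nor does any other criterion. If he is otherwise eligible, he can be allocated to either arm.

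**Step 5. Size.** The trial randomises 2 × 38 = 76 patients. The documents give neither the sex split nor the patients' plans to conceive, so no count of affected men can be derived.

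**The case against.** The strongest objection is that the places where men would naturally be instructed could not be read. Section 6.1 gives every patient a consent form, and section 3.0 attaches the package insert, but neither text was available. An instruction given at consent and not repeated in the eligibility list may be a sensible division of labour. This stands, and it limits the claim. A reader might infer that men in this trial get no advice about conception; the documents do not support that.

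A second objection is that the purpose of 4.7 is not stated. A rule protecting an existing pregnancy does not logically require one about later conception, and no period is given for men. This stands in part. The 8 weeks is the protocol's figure for women, and the right period for men cannot be settled from these documents. The difference in coverage between 4.2 and 4.7 remains.

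A third objection is that exclusion may not prevent exposure. Section 2.0 describes pre-emptive ribavirin for high-risk patients as existing practice, and inclusion 4.7 allows up to two aerosolised doses before enrolment. A man kept out of the trial might receive the drug anyway, so counselling matters more than exclusion. That is fair, and it is why the consent form needs checking as well. But the same could be said of women, for whom the sponsor still wrote 4.2.

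A reader might also try to put a number on the gap from the visit schedule. Section 7.3 says "All patients on the therapeutic arms will have a final visit 14 days" after end of therapy (± 1 day), so 56 − 14 = 42 of the 56 days in an 8-week period (75%) fall after that visit. This does not measure the defect. It applies the women's period to men, it describes visit timing and not eligibility, and it holds equally for women under 4.2. The 30-day limit in section 7.4 does not help either: it belongs to follow-up of patients who progress to pneumonia or stop for a serious adverse event, and is not general follow-up.

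**Conclusion.** The point holds as a minor mismatch in the eligibility text. Under section 4.0 as written, a man planning to conceive during or soon after ribavirin can be randomised, while a woman planning a pregnancy within 8 weeks after treatment cannot. The available sections neither explain nor correct this.

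The conclusion assumes that 4.7 is applied literally and that no appendix modifies it. If the consent form or Appendix D already instructs men, what remains is an eligibility line that could be brought into step with them.

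A reader might go further and infer that men should be required to use contraception. The documents do not support that: the available text sets no such requirement for either sex, and adding one for men alone would make their rule stricter than 4.2. The number of men affected is unknown and probably very small. Sample size, power and the planned analysis are untouched. This is an inexpensive safety improvement for the sponsor to consider, and no threat to the trial.

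**What to change.** Reword exclusion 4.7 to mirror 4.2, for example: *Men whose partner is pregnant, or who plan to father a child during treatment or within 8 weeks after its completion*, keeping the present restriction to randomised patients. If Appendix D gives a longer period for men, use that. Confirm that the consent form states the same period.

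The words on the treatment period go slightly beyond the letter of 4.2, whose planning clause names only the time after completion. Adding them to 4.2 as well would keep the two rules alike.

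The cost is one reworded line, one screening question and a check of the consent form. A very small number of otherwise eligible men may be lost; the documents give no basis for a figure. No statistical section needs to change.

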## 5.0 Treatment Plan

This is an open label randomised trial. All eligible patients will be randomized to receive ribavirin therapy either at the modified schedule of 60 mg/ml of the drug for a 3-hour period 3 times/day for at least 5 days by aerosolization via a SPAG-2 generator via a face mask **OR** patients will receive a one time loading dose of 10 mg/kg oral dose then 20 mg/kg orally (rounded to the nearest 200 mg dose) divided into three doses per day at a maximum of total dose of 1800 mg/day (therapeutic arms). The duration of either regimen is recommended to be up to 10 days but could be extended for more than 10 days at the discretion of the treating physician.

In addition, patients will receive inhalational bronchodilator therapy consistent of Xopenex 0.63 mg HHN every 6-8 hours as needed and as per standard of care. Patients may receive albuterol (2.5 mg per 3ml for adults) nebulization, if Xopenex is not tolerated. Patients will not be given IVIG or palivizumab for treatment of the RSV URI. Patients who develop evidence of LRI at any time will be considered reaching the primary endpoint and will be managed at the discretion of the treating physician as per standard of care (for example, patients can be treated by the standard or the modified aerosolized regimen with or without IVIG or palivizumab).

Patients with mild immunodeficiency who are at low risk (scoring of 0-2 on ISS) for progression and when treatment is not indicated for RSV URI as per standard of care (observational arm) will be followed prospectively once a week up to 4 weeks from the diagnosis of RSV.

For schedule of events tables see PDOL appendix I.

## **6.0 Pretreatment evaluation**

6.1 Patients will be identified based on eligibility criteria. After a patient is identified and expresses interest, the study will be explained by the study team and the informed consent form will be given to the patient to be signed.

6.2 All patients should have an initial nasopharyngeal wash positive for RSV by rapid testing and/or culture at onset of therapy unless a positive result was obtained from a specimen during the preceding 72 hours.

6.3 Routine blood tests will be obtained as per the standard of care within 48 hours of study entry as follows:

A. Hemoglobin, Hematocrit, WBC with differential if available, platelets count, pregnancy test from urine or blood for women of child-bearing potential.

B. Chemistry profile – BUN, Creatinine, Total bilirubin, Aspartate Aminotransferase (AST) and/or Alanine Aminotransferase (ALT), and alkaline phosphatase.

C. Nasal washes and blood at the time of enrollment will be taken and saved for testing for RSV viral loads and titers and neutralizing antibodies in serum at a later date (see section 7.1).

6.4 An initial history and physical examination.

6.5 A chest radiographic study (i.e. chest radiographs and/or CT scan of chest) will be obtained if not done within preceding 48 hours as per standard of care.

## **7.0 Evaluation During Study**

7.1 Nasal washes for the therapeutic arm will be repeated on day 3  $\pm$  1 day, day 7 ( $\pm$  1 days), day 14 ( $\pm$  1 days), and by day 14  $\pm$  1 days after end of therapy; and will be stored at 6-8 degrees Celsius until it can be taken to [name] laboratory for analysis. Blood specimens for the therapeutic arm will be drawn at enrollment and 14  $\pm$  1 days after end of therapy. These specimens will be shipped for batch analysis to [name] laboratory at Baylor College of Medicine ([name]) for viral loads, titers and for neutralizing antibodies testing (Please see references 7-9 for methods). For patients on the observational arm, nasal washes for RSV viral loads will be done once a week for 4 weeks and blood specimens will be taken at enrollment and the 4th week on study for neutralizing antibodies testing and for RSV viral load. Leftover of blood and nasal washes will be saved at [name] laboratory for future testing.

7.2 Routine blood tests as in 6.3 will be repeated at least once weekly until study is completed as part of the standard of care for patients who are on the therapeutic arms. Patients on observational arm will have routine blood tests done at enrollment and the 4th week on study.

7.3 Patients will be monitored for signs and symptoms of URI and LRI (Please see Appendix G and H for Clinical Assessment Tool). Patients who are hospitalized will be seen 2 times a week from the time of enrollment until discontinuation of ribavirin therapy. Patients who are not hospitalized will be monitored twice a week until the discontinuation of therapy or once a week for 4 weeks for patients on the observational arm. Any possible evidence of pulmonary infection should be confirmed by a repeat chest radiographic study and/or oxygen saturation level. All patients on the therapeutic arms will have a final visit 14 days  $\pm$  1 days after end of therapy.

7.4 Follow-up after end of therapy or discontinuation of therapy: Patients will be seen 14 days  $\pm$  1 days after discontinuation of therapy for the final determination of response, unless there is progression to pneumonia. In the latter scenario or if study drug is discontinued for Serious Adverse Events (SAEs), patients will be followed for up to 14 days from the time of occurrence of the event or until resolution of the SAE whichever occurs last or up to 30 days from the last dose of the study drug.

7.5 Physical Exams for the therapeutic arm will be done at day 3  $\pm$  1 day, day 7 ( $\pm$  1 days), day 14 ( $\pm$  1 days), and then 14 days ( $\pm$  1 days) after end of therapy. Concomitant medications that are used to treat LRI will be recorded day (3  $\pm$  1 day), day 7 ( $\pm$  1 days), and then at 14 days ( $\pm$  1 days) after end of therapy. Physical exams for observational arm will be done once a week for 4 weeks.

7.6 As standard of care, patients will have pulmonary function tests scheduled between 6-10 weeks after completing therapy for RSV.

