## Protocol Body

### 1.0 Objectives

Primary Objectives:

[figure not shown]
1) To determine whether oral ribavirin given for therapy of Respiratory Syncytial Virus (RSV) upper respiratory tract infection (URI) can prevent its progression to Lower respiratory tract Infection (LRI)-pneumonia, when compared to aerosolized ribavirin – modified regimen in HSCT recipients at moderate or high risk for progression.

Secondary Objectives:

- 1) To determine the safety of oral ribavirin therapy when compared to aerosolized ribavirin.
- 2) To calculate the cost effectiveness of using oral ribavirin when compared to aerosolized ribavirin.
- 3) To compare RSV viral loads in nasal washes and/or other respiratory specimens and RSV neutralizing antibodies in serum between patients on both arms of the study and a observational arm where low risk patients for progression are not receiving either regimen of ribavirin.

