## **9.0 Criteria for Removal from the Study**

9.1 Patients will be considered to have failed therapy if they develop evidence of pulmonary infection secondary to RSV (documented by chest radiographic study and/or Oxygen saturation level less than 90 mm Hg on room air). Therapy could be stopped or could be changed to either the standard or the modified regimen of aerosolized ribavirin if the patient is on the oral schedule and changed to the standard or continued on the modified regimen of aerosolized ribavirin if the patient is on the aerosolized regimen; all at the discretion of the primary care service. IVIG 500mg/kg every other day for 4 doses or Synagis (palivizumab) 15mg/kg as a single dose can be used in combination with aerosolized ribavirin.

9.2 Adverse events to ribavirin requiring discontinuation of therapy are: deterioration of respiratory function, abnormal liver function tests ( $>5$  x the upper normal limits), frequent bronchospasms not responding to bronchodilators, hypotension and cardiac arrest.

9.3 Anemia may occur due to ribavirin and therapy would be discontinued if there is evidence of severe hemolysis and/or the patient develops severe anemia as per the NCI classification i.e. Hemoglobin below 8 g/dl for more than 48 hours and does not respond to blood and/or blood products transfusion.

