### *Analysis*

We will use descriptive statistics to summarize the demographic and clinical characteristics of patients in each treatment arm and the observational arm.

We will use the Cochran-Mantel-Haenszel test stratified by risk group to test the null hypothesis stated above. We will also estimate the treatment failure rates with exact 95% binomial confidence intervals for each treatment arm.

We will tabulate adverse events for each treatment arm by severity and relationship to study therapy.

We will use descriptive statistics to summarize the costs associated with each treatment arm. Costs for each patient will be calculated as described in section 10.0 above.

We will use descriptive statistics to summarize the RSV viral loads and neutralizing antibodies for each treatment arm and the observational arm.

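### Anaemia, which Section 9.3 names as a ribavirin effect, is compared between arms only through reported adverse events; a by-arm haemoglobin and transfusion summary would be a cheap improvement

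*Combined protocol and SAP*

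**What the plan says.** **Objective.** Section 1.0, secondary objective 1: "To determine the safety of oral ribavirin therapy when compared to aerosolized ribavirin".

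**Entry.** Inclusion 4.6 says that patients with haemoglobin of 8 g/dl or more "would be eligible for the study even if they are currently receiving blood products". Exclusion 4.5 removes "patients with hemoglobin level less than 8 g/dl". Neither states a transfusion-free period before the qualifying value.

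**Stopping.** Section 9.3 has two limbs. The first: "Anemia may occur due to ribavirin and therapy would be discontinued if there is evidence of severe hemolysis". The second, joined to it by and/or, is severe anaemia, defined as "Hemoglobin below 8 g/dl for more than 48 hours and does not respond to blood and/or blood products transfusion".

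**Collection.** Haemoglobin is measured within 48 hours of entry (6.3) and at least weekly in the therapeutic arms (7.2). Section 7.5 says "Concomitant medications that are used to treat LRI will be recorded" at set visits. Transfusions are not mentioned there.

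**Analysis.** Section 11.0, Analysis: "We will tabulate adverse events for each treatment arm by severity and relationship to study therapy". Section 12.0 adds an interim safety review after each winter season, centred on serious adverse events. No other safety analysis is described.

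**Setting.** The trial is open label (5.0). Aerosol patients are hospitalised throughout therapy, while oral patients may be treated as outpatients (10.0). The independent panel in Section 8.0 is described for the pneumonia outcome only.

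**The concern.** The plan identifies anaemia as a drug effect, gives it its own stopping criterion and schedules the laboratory test that would show it. It then makes no analytic use of that test. What reaches the safety comparison is whatever an unblinded investigator reports as an adverse event, graded and attributed in transplant patients, some of whom are already transfused.

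Transfusion is both a consequence of anaemia and a treatment that corrects the laboratory value. If red-cell use differs between arms, haemoglobin-based reports can look alike while the underlying loss differs. At stake is the safety objective: a finding of similar anaemia would be hard to interpret without knowing how much transfusion it took to keep haemoglobin level.

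**Working it through.** **1. The plan's own figure.** The plan gives no figure for the safety comparison. Its sample size was set for pneumonia. On the success scale (80% and 85%) the variance term is 0.80 × 0.20 + 0.85 × 0.15 = 0.2875, and the distance from the margin is 0.05 + 0.10 = 0.15. With the futility look at half the information, the required drift is 1.7151, so n = 0.2875 × 1.7151² / 0.15² = 37.59, or 38 per arm, with nominal levels 0.6040 and 0.2116. All three match Section 11.0. The figure is not in dispute and is used below only as the number of patients per arm.

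**2. One patient followed through the text.**
- *Entry:* haemoglobin is at least 8 g/dl, possibly supported by blood products (inclusion 4.6). The enrolment value may already contain a transfusion effect.
- *On therapy:* haemoglobin falls and is corrected by transfusion. The second limb of 9.3 needs both more than 48 hours below 8 g/dl and no response to transfusion, so it is not met. The severe-hemolysis limb carries no transfusion condition and could still be met.
- *Laboratory record:* a fall present at a scheduled test is captured. A fall and correction between two weekly tests need not be.
- *Treatment record:* Section 7.5 covers LRI treatment. Whether the case report forms also ask for transfusions cannot be seen.
- *Analysis:* the fall counts only if reported as an adverse event. Section 11.0 has no haemoglobin change, lowest value or transfusion summary.

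**3. Illustration of the mechanism (every rate is assumed).** Let *pA* and *pO* be the true proportions with anaemia on aerosol and oral, and *m* the fraction of cases that transfusion keeps out of the comparison.
- Masking equal in both arms: observed difference = (1 − *m*)(*pO* − *pA*).
- Masking in the oral arm only: observed difference = *pO*(1 − *m*) − *pA*.

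| *pA* / *pO* | Masking | *m* = 0 | 0.25 | 0.50 | 0.75 |
|---|---|---|---|---|---|
| 10% / 40% | both arms | 30 | 22.5 | 15 | 7.5 |
| 10% / 40% | oral only | 30 | 20 | 10 | 0 |
| 20% / 40% | both arms | 20 | 15 | 10 | 5 |
| 20% / 40% | oral only | 20 | 10 | 0 | −10 |

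Entries are percentage points. Masking in the aerosol arm alone would act the other way: at 10% / 40% and *m* = 0.50 the observed difference is 40 − 10 × 0.50 = 35 points. Equal masking always shrinks the difference; unequal masking can shift it in either direction.

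**4. Precision.** With 38 per arm, the 95% half-width for a difference is 1.96 × √[(*pA*(1 − *pA*) + *pO*(1 − *pO*)) / 38]. At 10% / 40% this is 1.96 × √(0.33 / 38) = 0.183; at 20% / 40% it is 1.96 × √(0.40 / 38) = 0.201. Intervals of about ±18 to ±20 points suit estimation rather than proof of equal safety.

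**The case against.** The strongest reply is that anaemia is already visible in the plan, and much of that reply stands.

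- A reader might infer that excess haemolysis on oral ribavirin could show up only as extra red-cell units. The text does not support that. Severe haemolysis is a separate stopping criterion, haemoglobin and bilirubin are measured at least weekly, reported anaemia enters the table by severity as well as by relationship, and serious events reach the interim review.
- A reader might infer that transfusion disables the stopping rule. It affects only the haemoglobin limb.
- A reader might infer that transfusions go unrecorded. That is unproven: Appendices G and H and the schedule of events were not supplied, and silence in Section 7.5 on LRI treatment does not settle it.
- A reader might infer that admitting transfused patients biases the comparison. Randomisation balances transfusion support at entry in expectation. What remains is difficulty in reading the values, not bias at baseline.

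A further objection is that lowest haemoglobin, if collected, shows the fall, so nothing is hidden. This holds for falls present at a scheduled test. It does not hold for falls corrected between tests, so a transfusion measure is needed alongside the haemoglobin measure.

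Finally, hospitalised aerosol patients may be sampled and transfused more readily than oral outpatients, so a plain comparison of lowest values or of units could itself mislead. That objection is sound and shapes the fix. None of these points supplies the missing by-arm analysis.

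**Conclusion.** The point holds as a gap in the analysis plan: a named drug effect, with a laboratory measure already scheduled, is compared between arms only through reported adverse events. A difference in anaemia may therefore be understated. It would not be wholly lost, because reported events still count.

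The size of any masking is unknown. The documents give no anaemia rate, transfusion rate or masking fraction, and the table above shows only how the mechanism works under assumed values. The analysis gap is firm; the data-collection part depends on forms that were not supplied.

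The primary endpoint and sample size are unaffected. This is a cheap improvement to a secondary objective, not a flaw that threatens the trial.

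**What to change.** Add to Section 11.0, for the two therapeutic arms, each with a between-arm difference and 95% interval:

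- **(a)** change from enrolment to lowest haemoglobin, using only the scheduled tests under 6.3 and 7.2, so that extra inpatient sampling does not drive the result;
- **(b)** the proportion with haemoglobin below 8 g/dl or any red-cell transfusion after enrolment, together with red-cell units per patient.

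Show patients on blood products at entry separately, since (b) would otherwise count support that began before randomised treatment. Keep the adverse event table beside these summaries.

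If the case report forms do not already capture red-cell transfusions (date and units), add that item for both therapeutic arms. If they do, the change is one table.

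The cost is minor data entry. The write-up should caution that aerosol patients are hospitalised while oral patients may be outpatients, so monitoring and opportunity for transfusion may differ by arm. Eligibility and stopping rules are unchanged.
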